## 2.5. Justification for Dose

### 2.5.1. Doses for Escalation Phase Cohorts

The selection of the dosing strategy for dose escalation is based on non-clinical safety data and in vivo pharmacological evaluation in the cotton rat RSV prophylactic model. This approach is

supported by assessments of the PK profile of other RSV mAbs with YTE mutations. The wide dose range, from 300mg to 3000mg, in healthy adults would cover target exposures in infants and support PK/PD modeling to predict infant dosing.

RSM01 and nirsevimab were evaluated in the RSV cotton rat model. Collectively, the conclusion from those experiments is that the EC90s for RSM01 is similar to nirsevimab in term of PK/lung RSV titers. In the literature, nirsevimab has been reported to have a EC90 of 6.8  $\mu$ g/mL [Zhu 2017].

The human PK exposure of RSM01 in healthy participants was projected based on extrapolation made from the non-human primate PK in the toxicology studies and published reports of the PK characteristics of competitor monoclonal antibodies (nirsevimab and MK-1654) in healthy volunteers.

These projections suggest that following RSM01 doses of  $\geq$  300 mg the RSM01 concentration is predicted to be above the target EC90 threshold at Day 151.

RSM01 was well-tolerated in a definitive study in monkeys with a NOAEL of 300 mg/kg/dose or 100 mg/dose following IV or IM administration, respectively. The NOAEL at 300 mg/kg, IV, provided safety margins of approximately 10-fold and 1.1-fold to the starting dose of 300 mg IV and ending dose of 3000 mg IV, respectively, based on predicted human AUC. There were no test-article-related local reactions following administration of 100 mg/mL of RSM01 by IM injection in monkeys, which supports dosing of 600 mg, IM in humans at 100 mg/mL of RSM01.

Safety and PK data from the FiH study in adults are required to support proceeding to the target population of infants. The wide fixed-dose ranges to be tested in healthy adults will cover the anticipated target exposures in infants. The 300 mg dose in adults is estimated to correspond to the target dose of 50 mg in infants. Importantly, the maximum dose for the escalation cohorts (3000 mg IV) and the maximum dose for the Expansion Phase cohort (600mg IM) will provide necessary safety information to inform selection of doses in infants.

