Through Day 150 of follow-up, AEs occurred at similar frequencies between the mAb (804/968, 83%) vs. the Placebo (402/479, 83.9%) groups. SAEs were reported in 108/968 (11.1%) mAb vs. 81/479 (16.9%) Placebo recipients, and none were considered related to study drug. AESIs related to study drug were reported in 5/968 (0.5%) in nirsevimab vs. 3/484 (0.6%) in Placebo. There were no anaphylaxis or other notable hypersensitivity reactions. In the nirsevimab group, 4 infants experienced rash. One infant experienced one day of petechiae occurring 4 months after nirsevimab, which was not assessed by a health care provider. All 3 AESI infants in the Placebo group had rash.

AEs attributed to ADAs have not been observed in the nirsevimab trials. In the Phase 1 adult trial, ADA occurred at a similar frequency in the mAb and Placebo groups. At the baseline visit, 5/103 (4.9%) mAb vs. 3/34 (8.8%) Placebo recipients had ADA. During post-dose visits, 14/102 (13.7%) mAb vs. 5/33 (15.2%) Placebo recipients had ADA. In the nirsevimab Phase 1b/2a infant trial none had ADA at baseline and only the mAb group had ADA at post baseline (20/71, 28.2%) vs. 0/17 in the Placebo group. Aside from 2 infants with transient positive ADA at day 50, all positive ADAs occurred after the intended coverage duration of 150 days. ADA did not impact safety but lowered the drug exposure between days 150 to 360 in some infants.

The Phase 1 MK-1654 study randomized 152 healthy adults in a 3:1 ratio to MK-1654 (100mg IM, 300mg IM, 300mg IV, 1000mg IV and 3000mg IV) vs. Placebo. The overall safety profile of MK-1654 was similar to that of Placebo. No deaths, SAEs, discontinuations due to AEs, clinically significant laboratory AEs, or dose-dependent pattern of drug-related AEs were reported [Aliprantis 2020].

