## Safety

With 6 participants (per RSM01 arm in each Dose Escalation Phase cohorts), there is approximately 80% (90%) power to observe at least one AE if the true AE rate is 23.53% (31.87%).

With 24 participants (across all doses of RSM01 in the Dose Escalation Phase cohorts or the Dose Expansion Phase cohort), there is approximately 80% (90%) power to observe at least one AE if the true AE rate is 6.49% (9.15%).

Across all doses of RSM01 (48 participants), there is approximately 80% (90%) power to observe at least one AE if the true AE rate is 3.3% (4.68%).

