9.6.1 Terms and Definitions

The detection of ADA to RSM01 will be performed using a validated immunoassay method with tiered testing of screening, confirmatory, and titration, i.e.:

1. All samples will undergo a screening test.
2. If the screening test is positive for ADA, the sample will undergo a confirmatory test. A sample that has a negative or not reportable (NR) screening result will not undergo further testing.
3. If the confirmatory test is positive, the sample will be analyzed to determine the titer. A titer result can be a quantifiable number or not reportable (“titer not reportable” or “TNR”).

The following terms and definitions will be applied in the immunogenicity analyses.

ADA status of a sample

- Baseline ADA negative sample: Screening or confirmatory test of the last sample before administration of study treatment indicates ADA is not detected.
- Baseline ADA NR sample: Screening or confirmatory test of the last sample before administration of study treatment indicates ADA is not reportable.
- Baseline ADA missing: No baseline sample was available for testing.
- Baseline ADA positive sample: Screening and confirmatory tests of the last sample before administration of study treatment indicates ADA is detected. The numeric titer will be reported unless the titer result is NR, which would be reported as positive TNR.
- Post-baseline ADA negative sample: Screening or confirmatory test of sample taken after administration of study treatment indicates ADA is not detected.

- Post-baseline ADA NR sample: Screening or confirmatory test of sample taken after administration of study treatment indicates ADA is not reportable.
- Post-baseline ADA missing: No post-baseline sample was obtained.
- Post-baseline ADA positive sample: Screening and confirmatory tests of sample taken after administration of study treatment indicates ADA is detected. The numeric titer will be reported unless the titer result is NR, which would be reported as positive TNR.

ADA status of a participant

- Baseline ADA negative participant: A participant with baseline ADA negative sample. A participant with NR or no baseline ADA sample is assumed to be baseline ADA negative.
- Baseline ADA positive participant: A participant with a baseline ADA positive or positive TNR sample.
- Post-baseline ADA positive participant: A participant with at least one post-baseline ADA positive or positive TNR sample. An ADA positive participant will be further classified as follows:

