 - Treatment-emergent positive: Participant had a post-baseline ADA positive or positive TNR sample in a participant with a baseline ADA negative sample OR participant had a post-baseline ADA positive sample that is \geq 8-fold increase above baseline titer in a participant with a baseline ADA positive sample. Note that the baseline sample and at least one post-baseline sample must have reportable titer to assess whether pre-existing immunogenicity was treatment-boosted.
 - Treatment-emergent nonevaluable.
 - Treatment-emergent negative.
- Post-baseline ADA negative participant: A participant with no post-baseline ADA positive or positive TNR sample.
- Any ADA detected: Subjects in Baseline ADA Positive AND/OR Treatment-emergent.
- No ADA Detected: Subjects who are Baseline ADA negative AND either Post-baseline ADA negative OR no valid post-baseline results (excluded from immunogenicity population).

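### The SAP calls an undetected post-dose ADA result negative whatever the RSM01 level in the sample, although drug is predicted to be present at every planned post-dose ADA visit in RSM01 recipients

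*SAP*

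**What the plan says.** SAP 9.6.1 defines the sample result as "Post-baseline ADA negative sample: Screening or confirmatory test of sample taken after administration of study treatment indicates ADA is not detected". A participant is post-baseline negative when no post-baseline sample is positive. Table 1 in SAP 9.6.2 derives each sample result from the screening, confirmatory and titer results alone, and Table 2 builds the participant result from those. No step uses a drug concentration. Table 1 also derives a missing screening result as negative.

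SAP 9.6.1 lists a class "Treatment-emergent nonevaluable" without defining it. It sits beneath the post-baseline ADA-positive participant, and Table 2 never assigns it.

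On drug levels, Protocol 2.5.1 says that for doses of 300 mg and above "the RSM01 concentration is predicted to be above the target EC90 threshold at Day 151". All RSM01 arms are at 300 mg or more. Under the protocol's schedules (1.3), post-dose ADA samples fall on Days 15, 29, 61, 91, 121 and 151 in Cohorts 1-4 and on Days 29, 91 and 151 in Cohort 5. PK is drawn at each of those visits in both serum and VAMS. Participation ends at Day 151 (Protocol 4.2).

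The assay is described as validated and tiered. No drug-tolerance limit is stated for either matrix.

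**The concern.** An ADA immunoassay can miss antibody when the sample holds more drug than the assay tolerates. A result of not detected then means either no ADA or ADA that could not be seen. The plan has no post-dose sample in an RSM01 recipient at a time when drug is predicted to be gone, and its derivation does not separate the two meanings.

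Three outputs are exposed:

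- **Incidence.** ADA incidence through Day 151 is a secondary endpoint, summarised by treatment group. A low rate in an arm could reflect the assay and not the antibody.
- **The placebo contrast.** Placebo recipients are in the immunogenicity population and carry no RSM01, so any masking would act on one side only.
- **Subgroups.** Masked participants would enter the *No ADA detected* group used for the AE summary (SAP 9.6.3) and the ADA-negative side of the concentration summaries (SAP 8.1).

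**Working it through.** **The plan's own figure.** The only probabilities stated are for seeing at least one AE, 1 − (1 − p)^n. With n = 6 and p = 23.53% (31.87%) this gives 80% (90%). With n = 24 and p = 6.49% (9.15%), and with n = 48 and p = 3.3% (4.68%), it again gives 80% (90%). These reproduce. Nothing comparable is stated for ADA.

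**Inputs from the documents**

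- EC90: "nirsevimab has been reported to have a EC90 of 6.8" µg/mL, with RSM01 described as similar (Protocol 2.5.1).
- Arm sizes: 6 RSM01 recipients in each of Cohorts 1-4 and 24 in Cohort 5.
- Cohort 5 dose: 300 to 600 mg IM, not yet fixed.
- Scaling: predicted AUC margins are about 10-fold at 300 mg IV and 1.1-fold at 3000 mg IV. The AUC ratio is 10 / 1.1 = 9.1 for a 10-fold dose, so close to linear.

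**Inputs assumed**

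- The Day 151 level at 300 mg sits at the EC90, which is the lowest level consistent with the prediction.
- PK is dose-linear.
- Half-life is 60 days; no human half-life for RSM01 is given.
- Tolerance limits from 5 to 250 µg/mL are tried, since none is stated.
- Levels are in serum terms. The secondary endpoint uses VAMS, and the documents give no conversion.

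**Floor concentrations.** C(d) = 6.8 × (dose / 300) × 2^((151 − d) / 60), in µg/mL:

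| Dose | D15 | D29 | D61 | D91 | D121 | D151 |
|---|---|---|---|---|---|---|
| 300 mg | 32.7 | 27.8 | 19.2 | 13.6 | 9.6 | 6.8 |
| 1000 mg | 109.1 | 92.8 | 64.1 | 45.3 | 32.1 | 22.7 |
| 3000 mg | 327.2 | 278.4 | 192.3 | 136.0 | 96.2 | 68.0 |

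At 600 mg the Day 151 floor is 13.6.

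**Samples.** There are 24 × 6 = 144 planned post-dose samples in Cohorts 1-4 and 24 × 3 = 72 in Cohort 5, so 216 in all. With Cohort 5 at 300 mg, 168 (78%) exceed a tolerance of 10 µg/mL, 54 (25%) exceed 50, 30 (14%) exceed 100 and 12 (6%) exceed 250.

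**Participants, which is the unit of the endpoint.** A participant lacks a conclusive negative only if every post-dose sample exceeds the limit. With complete sampling the Day 151 level decides this, so these counts do not depend on the half-life.

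| Tolerance (µg/mL) | No sample on which a negative is conclusive | Which arms |
|---|---|---|
| 5 | 48/48 | all |
| 10 | 12/48 | 1000 and 3000 mg; 36/48 if Cohort 5 gets 600 mg |
| 50 | 6/48 | 3000 mg |
| 100 or more | 0/48 | none |

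A missed Day 151 visit raises the count. In Cohort 5 at 300 mg, for example, the last remaining level would be 13.6 at Day 91, above a limit of 10.

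**Dose gradient.** At Day 151 the arms differ only if the limit lies between about 7 and 68 µg/mL. Below that all arms are affected alike. Above it none is, at the floor levels.

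**What a zero would mean.** Take the post-dose ADA rate in the adult nirsevimab study cited in Protocol 2.6, 14/102 = 13.7%, as an illustration. With n = 6, the chance of at least one positive is 58.8% at full detection, 34.7% if half of the positives are detected and 18.9% if a quarter are. For 0/6 the exact 95% upper limit is 1 − 0.025^(1/6) = 45.9%.

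**The case against.** The best counter-argument is that the problem may not exist. The tolerance limit is not in the documents, and at 100 µg/mL or more the rule would change no participant's class in this model. The drug levels are projections from animals and other antibodies, and Protocol 2.5.2 itself allows for a shorter half-life than the comparators. All of that stands, and it makes the bias conditional.

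Some information is already planned. Concentrations are summarised by ADA status, ADA status and titers appear on individual PK profiles (SAP 8.1), and sample-level ADA listings are produced. A careful reader could compare negatives with drug levels, but none of these outputs changes a negative or the incidence table. The laboratory might return *not reportable* for interference. The SAP does not say when that result is used, so this can be neither relied on nor ruled out.

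The trial is descriptive, and 0/6 is weak evidence of low immunogenicity even with a perfect assay. That limits the harm. It does not make the label right, because the 45.9% limit assumes that the six negatives are real.

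A reader might also infer more than the documents support:

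- *That all ADA samples contain drug.* Day 1 samples are pre-dose and placebo samples hold none.
- *That up to 78% of the endpoint data are affected.* That is a share of samples. At the same tolerance of 10 µg/mL the participant count is 12/48.
- *That the infant nirsevimab trial shows masking.* Protocol 2.6 reports that "all positive ADAs occurred after the intended coverage duration of 150 days", but with an exception for two infants with transient positives at Day 50. It concerns another antibody, and the protocol does not attribute the timing to drug interference.

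**Conclusion.** The point holds as a gap in the classification rule. Drug is predicted to be present at every planned post-dose ADA visit in RSM01 recipients, a paired PK sample is planned at each of those visits, and the SAP calls an undetected result negative without using it. If levels exceed the assay's tolerance, incidence could be understated and the placebo contrast and ADA subgroups distorted.

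The size ranges from all 48 RSM01 participants at a limit of 5 µg/mL to none at 100 or more. At 10 µg/mL the answer turns on the Cohort 5 dose (12 or 36 of 48). These figures rest on the assumed 6.8 µg/mL floor, linear PK, complete sampling and serum terms. Actual levels may be higher or lower, and no VAMS figure can be derived.

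It is tempting to conclude that incidence will be understated, and most of all at 3000 mg. The documents do not show that. A gradient across doses at Day 151 needs a limit of about 7 to 68 µg/mL, and whether the real limit lies there is unknown. This is a cheap improvement to a secondary endpoint, not a defect in the primary safety analysis.

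**What to change.** 1. State the validated drug-tolerance limit of the ADA assay for VAMS and for serum.
2. In SAP Table 1, derive a post-baseline negative screening or confirmatory result as *Inconclusive* when the measured RSM01 concentration from the same visit and matrix exceeds that limit. Use raw PK results, so that a value below quantification counts as below the limit; SAP 8.1 sets such values to missing for its summaries once drug has been quantified. Flag a missing paired concentration as not assessable.
3. Do not let a post-baseline missing screening result count as a conclusive negative.
4. In SAP Table 2, add a separate participant class, *ADA inconclusive*, for those with no positive and no conclusive negative post-baseline sample. Do not reuse the nonevaluable label, which belongs to ADA-positive participants. Keep baseline-negative members of the new class out of *No ADA detected* in SAP 9.6.1 and 9.6.3.
5. Report incidence by treatment group over all participants and over evaluable participants, with the number inconclusive.

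The cost is SAP wording and a merge of PK and ADA data already planned, with no new samples. Evaluable denominators would shrink, mainly at 1000 and 3000 mg. If the tolerance proves high, the results do not change.

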9.6.2 Derivation Rules

Based on the definitions provided in Section **Error! Reference source not found.**, immunogenicity results will be collected prior to dose administration and at post-treatment follow-up visits. Immunogenicity results will be collected prior to dose administration and at post-treatment follow-up visits. Sample-level and participant-level derivations are shown in Tables 1 and 2, respectively.

Table 1: Algorithm for Deriving of Anti-Drug Antibody Sample-Level Results

SDTM raw data			Derived ADaM sample result
ADA Screening Result (ISTSTOPO=Screen)	ADA Confirmatory Result (ISTSTOPO=Confirm)	ADA Titer Result (ISTSTOPO=Quantity)	
Negative	NA	NA	Negative
NR	NA	NA	NR
Missing	NA	NA	Negative
Positive	Negative	NA	Negative
Positive	NR	NA	NR
Positive	Positive	Number	Number
Positive	Positive	NR	Positive TNR

ADaM = analysis data model, NA = not applicable, NR = not reportable, SDTM = study data tabulation model, TNR = titer not reportable.

Table 2: Algorithm for Deriving Anti-Drug Antibody Participant-Level Results

ADaM data across samples		Participant-level ADaM result		
Baseline ADA result	Post-baseline ADA results	Derived baseline ADA	Derived post-baseline ADA	Treatment-emergent
Negative or NR or Missing	At least one Negative, no Number or Positive TNR	Negative	Negative	Negative
Negative or NR or Missing	All NR or Missing	Negative	NA	NA
Negative or NR or Missing	At least one Positive TNR, no Number	Negative	Positive TNR	Treatment-emergent
Negative or NR or Missing	At least one Number	Negative	Positive	Treatment-emergent
Positive TNR	At least one Negative, no Number of Positive TNR	Positive TNR	Negative	Neither
Positive TNR	All NR or Missing	Positive TNR	NA	NA
Positive TNR	At least one Positive TNR, no Number	Positive TNR	Positive TNR	TNR
Positive TNR	At least one Number	Positive TNR	Positive	TNR
Number	At least one Negative, no Number or Positive TNR	Positive	Negative	Negative
Number	All NR or Missing	Positive	NA	NA
Number	At least one Positive TNR, no Number	Positive	Positive TNR	TNR
Number	At least one Number, but none \geq	Positive	Positive	Negative

ADaM data across samples		Participant-level ADaM result		
Baseline ADA result	Post-baseline ADA results	Derived baseline ADA	Derived post-baseline ADA	Treatment-emergent
	8-fold increase above baseline titer			
Number	At least one Number \geq 8-fold increase above baseline titer	Positive	Positive	Treatment-emergent

ADaM = analysis data model, NA = not applicable since not in immunogenicity population, NR = not reportable, SDTM = study data tabulation model, TNR = titer not reportable.

The number and percentage of participants will be reported as follows:

- Baseline ADA positive vs. negative in the Immunogenicity Population
- Post-baseline ADA positive among participants with at least one post-baseline ADA sample
 - Treatment-emergent ADA
 - Negative treatment-emergent

Listings will be prepared with ADA sample-level and participant-level results.

9.6.3 Potential Association of Immunogenicity with Adverse Events

A summary of AEs showing frequency and percentage of participants with AEs will be produced for the following subgroups:

- Any ADA detected
- No ADA detected

10. Missed Assessments due to COVID-19

All visits or assessments missed due to COVID-19 will be presented in a listing.

11. Interim Analysis

An interim analysis is planned after availability of Cohort 2, Cohort 3, and Cohort 4 Day 30 data.

An interim analysis with a formal Safety report is planned for this study when all participants in each of the Dose Escalation Phase cohorts have completed Day 91. In addition, SDTM datasets will be prepared for interim PK modeling. An Interim Report will be prepared when the results from Day 91 become available. Additional interim analyses may occur prior to the primary analysis to aid in the development of individual and population PK models to predict dose levels in infants and assess covariates.

The purpose of this interim analysis will be a strategic review to inform the broader program and future development plans, including the determination of the potential dose of RSM01 in infants. No decision directly related to this study will be made from the results of this interim analysis. Agreement on the analysis plan, unblinding procedures, specific outputs, method of distribution,

the level of data cleaning and details of whom the results will be provided to will be outlined in a separate unblinding plan (which will be finalized prior to the interim analysis).

Firewalled roles will be involved in the interim analysis to create unblinded datasets and perform analyses. The investigator will remain blinded. The sponsor will review blinded (pooled) safety data by cohort and unblinded aggregated PK data by treatment group (RSM01 vs. placebo) within and across cohorts. The sponsor will be blinded at the participant level throughout the study. An unblinding plan will be prepared to include unblinding details.

12. Changes in the Planned Analysis

Any changes from this statistical analysis plan that are not documented in a formal SAP amendment will be documented in the CSR for this study.

13. Change of Statistical Programming Service Provider

In May 2022, Gates MRI decided to terminate the RSM01-101 biostatistics and statistical programming contract with its original service provider. Gates MRI assumed responsibility for statistical oversight of the study, including finalization of the SAP, and initiated a new agreement with another service provider for the statistical programming of SDTM and ADaM datasets as well as tables, figures, and listings. In its statistical oversight, Gates MRI will follow statistical principles that are consistent with the International Conference on Harmonisation (ICH) guidelines E9 (Statistical Principles for Clinical Trials) and apply the following procedures:

- Prior to an interim unblinded data review, Gates MRI will finalize an unblinding plan that describes the purposes for unblinding, the roles and responsibilities of team members who will be involved in the unblinding steps and the preparation and review of unblinded analyses, and the level of access each role will have to unblinded interim data (i.e., fully blinded, blinded except emergency participant-level unblinding, unblinded to aggregate results, or unblinded to participant-level results);
- Prior to an interim unblinded data review, Gates MRI will finalize a statistical analysis plan that describes all analyses that will be included in the clinical study report; and
- Gates MRI will rely on the new service provider to initiate unblinding as described in their SOP, including use of the new service provider's unblinding authorization form.

Gates MRI is currently in the process of establishing SOPs associated with unblinding and statistical analysis plans.

New data transfer agreements have been established to allow blinded and unblinded data transfers between Gates MRI and the data management, statistical programming, and PK vendors, as described in a separate Unblinding Plan. All of the service providers have continued to follow their respective standard operating procedures (SOPs) for establishing and maintaining the necessary firewalls to protect the study blind.

14. References

Protocol Gates MRI-RSM01-101. A Phase 1 Randomized, Double-blind, Placebo-Controlled Study to Evaluate the Safety, Tolerability, and Pharmacokinetics of Single Ascending Doses of RSM01, a Monoclonal Antibody Targeting Respiratory Syncytial Virus, in Healthy Adults, Protocol Version 4.0, 21 Jan 2022.

FDA, Guidance for Industry: Immunogenicity Assessment for Therapeutic Protein Products ([name], August 2014).

EMA, Guideline on Immunogenicity assessment of therapeutic Proteins – Revision 1 (London, UK, May 2017).

15. Schedule of Assessments

Schedule of Activities for the Dose Escalation Phase (Cohorts 1-4)

Visits	Screen	Pre-V1	V1	V2	V3	V4	V5	V6	V7	V8	V9	V10	V11	Dis-con Visit ⁹
Study Day and Visit window days (d)	D-30 to D-2d	D-1 ±0d	D1 ±0d	D2 ±0d	D3 ±0d	D6 ±1d	D8 Day 8-10	D15 ±3d	D2 9 Day 29-35	D61 ±7d	D91 ±7d	D121 ±7d	D151 ±7d	
Activities:														
Informed consent	X													
Check/verify eligibility criteria	X	X	X											
Confinement ¹		X	X	X	X									
Demography, full medical history, PE, height, weight	X													
Focused PE		X	X	X	X	X	X	X	X	X	X	X	X	X
Serum pregnancy test ²	X	X												X
HIV antibody and Hepatitis B & C test	X													
Urine drug screen	X	X												
Urinalysis	X	X						X			X		X	X
Safety laboratory assessments ³	X	X					X				X		X	X
12-lead electrocardiogram (ECG), performed intruplicate ⁴	X			X										
Vital signs ⁵	X		X	X	X									X
Randomization ⁶			X											
Study intervention administration ⁷				X										
Distribute/review diary cards					X									
Collect diary card							X							
Distribute memory aid						X	X	X	X	X	X	X	X	
Collect memory aid							X	X	X	X	X	X	X	X
Record solicited AEs (local for IM doses only, &systemic) through Day 7			X	X	X	X								
Record unsolicited AEs, AESIs, and SAEs	X	X	X	X	X	X	X	X	X	X	X	X	X	X
Record concomitant medications		X	X	X	X	X	X	X	X	X	X	X	X	X

Schedule of Activities for the Dose Escalation Phase (Cohorts 1-4)

Visits	Screen	Pre-V1	V 1	V 2	V 3	V 4	V 5	V 6	V7	V 8	V 9	V10	V11	Discon Visit ⁹
Study Day and Visit window days (d)	-30 to -2d	D-1	D1 ±0d	D2 ±0d	D3 ±0d	D6 ±1d	D8 Day 8-10	D15 ±3d	D29 Day 29-35	D61 ±7d	D91 ±7d	D121 ±7d	D151 ±7d	
Activities:														
Serum and VAMS sample for PK ⁸			X	X	X	X	X	X	X	X	X	X	X	X
Serum and VAMS sample for ADAs ⁸			X					X	X	X	X	X	X	X
Serum and VAMS sample for RSV nAb levels ⁸			X							X		X	X	X

V = Visit; D= Day; PE= physical examination; HIV= Human immunodeficiency virus; IM= intramuscular; AE=adverse event, SAE=serious adverse event; AESI=AE of special interest; PK= pharmacokinetics; ADA = anti-drug antibodies; VAMS = volumetric absorptive microsampling RSV mAb = Respiratory Syncytial Virus neutralizing antibody

¹ Confinement- participants will be confined to study site from Day -1 to after completion of Day 3 assessment (a total of 3 nights). All Day 1 assessments and sample collections are prior to study intervention.

² In addition to scheduled pregnancy tests in female participants, if pregnancy is suspected during the study, a serum test will be done.

³ Safety laboratory testing includes serum chemistry and hematology.

⁴ All 12-lead ECGs will be obtained after the participant has rested in a supine position for at least 10 minutes. Triplicate ECGs will be taken approximately one minute apart. Refer to Protocol section 8.1.6 for details. The window for obtaining the initial ECG is ± 15 minutes.

⁵ Day 1 vital signs will be taken pre-dose before blood sample collection, and 1 hour, 4 hours and 8 hours after IM dose and at pre-dose, 15, 30 and 45 minutes, 1 hour, 1.5 hours, 2 hours, 4 hours, and 8 hours after IV dose. The window for vital signs measurements is ± 3 minutes. Refer to Protocol section 8.1.2.1. Vital Signs for details. On Day 2, vital signs will be taken at 24 hours post-dose. The window for these measurements is ± 0.5 hours. On Day 3, vital signs will be taken at 48 hours after dosing. The window for these measurements is ± 1.0 hours.

⁶ The first participant in each cohort (Cohorts 1-4) will receive RSM01without being randomized.

⁷ On any given day, participants should be dosed at least 2 hours apart, after the first sentinel participant is dosed with RSM01, and 24 hours has passed. The ≥2-hour wait time between IV infusions is to begin at the end of the previous infusion.

⁸ Blood samples for PK assessments on Day 1 (Visit 1) will be drawn at pre-dosing 1 hour (+/- 30 minutes) before administration of IM injection or beginning of infusion,, at 5 minutes (± 1 minute) after end of infusion for IV doses only, and at 8-hours (±0.5 hour) and 24-hours (±1 hour) after end of infusion for IV doses and at 8-hours (±0.5 hour) and 24-hours (±1 hour) after IM doses. ADA and RSV neutralizing antibody on Day 1 (Visit 1) will be drawn pre-dose only 1 hour (+/- 30 minutes) before administration of IM injection or beginning of infusion.

⁹ Early Discon= A discontinuation visit will be scheduled for participants who discontinue or withdraw, whenever possible.

Schedule of Activities for the Expansion Phase (Cohort 5)

Visits	Screen	Pre-V1	V 1	V 2	V 3	V 4	V 5	Discon visit ⁸
Study Day and Visit window days (d)	D-30 to D-1d	Day -1	D1	D8	D29	D91	D151	
Activities:			±0	Days 8-10	Days 29-35	±7d	±7d	
Informed consent	X							
Check/verify eligibility criteria	X	X	X					
Confinement ¹		X	(X)					
Demography, full medical history, PE, height, weight	X							
Focused history/PE			X	X	X	X	X	X
Serum pregnancy test ²	X	X						X
HIV antibody, Hepatitis B and C	X							
Urine drug screen	X	X						
Urinalysis	X	X		X		X	X	X
Safety laboratory assessments ³	X	X		X		X	X	X
12-lead ECG (performed in triplicate) ⁴	X							
Vital signs ⁵	X		X					X
Randomization			X					
Study intervention administration ⁶			X					
Distribute/review diary cards			X					
Collect diary cards				X				
Distribute memory aid			X	X	X	X		
Collect memory aid				X	X	X	X	X
Record solicited AEs (local & systemic)			X					
Record unsolicited AEs, AESIs and SAEs	X	X	X	X	X	X	X	X
Record concomitant medications		X	X	X	X	X	X	X
Serum and VAMS sample for PK ⁷			X	X	X	X	X	X
Serum and VAMS sample for ADAs ⁷			X		X	X	X	X
Serum and VAMS for RSV nAb levels ⁷			X			X	X	X

V = Visit; D= Day; PE= physical examination; HIV= Human immunodeficiency virus; IM= intramuscular; AE=adverse event, SAE=serious adverse event; AESI=AE of special interest; PK= pharmacokinetics; ADA = anti-drug antibodies; VAMS = volumetric absorptive microsampling; RSV mAb = Respiratory Syncytial Virus neutralizing antibody

¹Confinement = participant should present to the clinic within 24 hours of Day -1 visit and will stay at the clinic on the Pre-V1, Day -1(i.e., the night before the Day 1 visit). (X)= A second overnight stay for the night of Day 1 is optional, based on investigator's decision. If participant is confined on the night of Day 1, vital signs will be taken 24 hours post-dose.

²In addition to scheduled pregnancy tests in female participants, if pregnancy is suspected at any time during the study, a serum test will be done.

³ Safety laboratory assessments includes serum chemistry and hematology.

⁴ 12-lead ECGs will be obtained after the participant has rested in a supine position for at least 10 minutes. Triplicate ECGs will be taken approximately one minute apart. Refer to Protocol section 8.1.6 for details.

⁵ Day 1 vital signs will be taken before dose and again 4 hours after dose. The window for vital signs measurements is \pm 3 minutes. Refer to Protocol section 8.1.2.1. Vital Signs for details.

⁶ All Day 1 safety assessments and sample collections will be done prior to study intervention. Symptom assessments will be done after dosing. Following dose administration, if the participant will not be confined overnight for the optional night of Day 1, they will be observed for at least 4 hours at the study site after receiving the study intervention, for safety monitoring.

⁷ Blood samples for PK, ADA and RSV neutralizing antibody at Day 1 will be drawn at pre-dose only 1 hour (+/- 30 minutes) before administration of IM injection.

⁸ Early Discon = A discontinuation visit will be scheduled for participants who discontinue or withdraw, when possible.
